### Tertiary efficacy endpoints

The following tertiary efficacy endpoints will be assessed among evaluable subjects and the FAS:

- PSA: PSA will be obtained during routine laboratory assessments and results at each scheduled assessment will be compared to baseline along with percentage change from baseline.
- QoL: QoL will be obtained using the EQ-5D-5L, with each scheduled assessment compared to baseline.
- CTCs: The number of CTCs will be obtained at each scheduled assessment and compared to baseline.

Protocol: A Phase 2 Open Label, Multi-Center, Multinational Study Investigating The Efficacy and Safety Of GTx-024 On Advanced, Androgen Receptor-Positive Triple Negative Breast Cancer (AR+ TNBC)	Compound No.: GTx-024 Author: [name]
---	---

- Duration of prior CB: the impact of duration of prior CB on outcome (CB response at weeks 16 and/or 24, PFS, TTP, duration of response).
- Time from diagnosis of metastases to enrollment: the impact of time from diagnosis of metastases to study enrollment on outcome (CB response at weeks 16 and/or 24, PFS, TTP, duration of response).
- Tumor volume and change from baseline in tumor volume.
- Pharmacokinetics: GTx-024 and GTx-024 glucuronide plasma concentrations and outcome (CBR at weeks 16 and/or 24).

### Safety endpoints

The following safety endpoints will be assessed among evaluable subjects as well as all subjects enrolled and treated:

- AEs and concomitant medications.
- Laboratory examinations (clinical chemistry, hematology, and urinalysis).
- Physical examinations.
- Vital signs.
- ECOG performance status.
- ECG parameters.

### Pharmacokinetic endpoints

- Plasma concentrations of GTx-024 18 mg and GTx-024 glucuronide at each assessment.

## 11.4.3 Statistical methodology

### 11.4.3.1 Demographic data

Continuous demographic data (i.e., age, weight, height, and body mass index [BMI]) will be summarized by descriptive statistics (arithmetic mean, standard deviations, median, minimum, maximum, and total number of subjects). Categorical demographic data (i.e., gender, race,

Protocol: A Phase 2 Open Label, Multi-Center, Multinational Study Investigating The Efficacy and Safety Of GTx-024 On Advanced, Androgen Receptor-Positive Triple Negative Breast Cancer (AR+ TNBC)	Compound No.: GTx-024 Author: [name]
---	---

ethnicity, and ECOG performance status) will also be listed and tabulated in frequency counts and percentage.

#### 11.4.3.2 Primary efficacy analysis

The primary efficacy analysis is based on rules as set forth in Simon's two-stage (optimal) design as previously described, and is based on the proportion of evaluable subjects in the FAS who achieve CB at 16 weeks. At least 2/21 subjects must achieve CB in order for the trial to proceed to the second stage. If the trial proceeds to the second stage,  $\geq 5/41$  subjects must have CB at 16 weeks to deem the efficacy criteria to have been met. This is the minimum number of successes needed to rule out an unacceptably low, 5%, CB rate (lower limit of the 90% confidence interval). The exact 90% and 95% confidence intervals about the CBR at week 16 will be constructed.

#### 11.4.3.3 Secondary efficacy analysis

- The exact 90% and 95% confidence intervals about the CBR at week 16 among subjects in the FAS will be constructed.

The following secondary efficacy analyses will be performed, if not already done so above, among the evaluable subjects, the FAS, and the PPS:

- The exact 90% and 95% confidence intervals about the CBR at 16 and 24 weeks will be constructed.
- The exact 95% confidence interval about the ORR (PR or CR) will be constructed at weeks 16 and 24.
- The exact 95% confidence interval about the BOR will be constructed at weeks 16 and 24.
- PFS: Median PFS and 95% confidence intervals will be estimated by the Kaplan-Meier method and the survival function and associated 95% confidence intervals will be constructed at key time points.
- TTP: Median TTP and 95% confidence intervals will be estimated by the Kaplan-Meier method and the survival function and associated 95% confidence intervals will be constructed at key time points.
- Duration of response: Median duration of response and 95% confidence intervals will be estimated by the Kaplan-Meier method and the survival function and associated 95% confidence intervals will be constructed at key time points for responders.

Protocol: A Phase 2 Open Label, Multi-Center, Multinational Study Investigating The Efficacy and Safety Of GTx-024 On Advanced, Androgen Receptor-Positive Triple Negative Breast Cancer (AR+ TNBC)	Compound No.: GTx-024 Author: [name]
---	---

- Overall Survival: Median OS and 95% confidence intervals will be estimated by the Kaplan-Meier method and the survival function and associated 95% confidence intervals will be constructed at key time points. Follow up will be up to 24 months post treatment initiation for each subject and subjects alive at that time will be censored.

#### 11.4.3.4 Tertiary efficacy analysis

The following tertiary efficacy analyses apply to the evaluable subjects and the FAS:

- PSA changes from baseline to each scheduled assessment will be described and tested for a significant change from baseline. Percentage change from baseline will be summarized and analyzed as well.
- QoL: The EQ visual analog scale (VAS) will be summarized by descriptive statistics at baseline and each assessment. Mean changes from baseline will also be summarized using descriptive statistics and 95% confidence intervals. EQ-5D-5L single item scale scores (mobility, self-care, usual activities, pain/discomfort, and anxiety/depression) will be summarized by means of frequency counts at baseline and at each assessment.
- CTCs: changes in the number of CTCs from baseline to each scheduled assessment will be described and tested for a significant change from baseline.
- Duration of prior CB: the impact of duration of prior CB on the current CB response will be explored in an exploratory way using logistic regression models with and without other covariates. The impact of duration of prior CB on PFS, TTP, and duration of response outcomes will be assessed in a Cox proportional hazards model with and without other covariates.
- Time from diagnosis of metastases to enrollment: the impact of time from diagnosis of metastases to study enrollment on the current CB outcome will be explored in an exploratory way using logistic regression models with and without other covariates. The impact of time from diagnosis of metastases to study enrollment on PFS, TTP, and duration of response outcomes will be assessed in a Cox proportional hazards model with and without other covariates.
- Tumor volumetrics: the effect of GTx-024 18 mg on tumor volume will be described visually using waterfall plots.
- GTx-024 and GTx-024 glucuronide plasma concentrations will be assessed for their association with CBR at weeks 16 and 24 using logistic regression by creating binary

Protocol: A Phase 2 Open Label, Multi-Center, Multinational Study Investigating The Efficacy and Safety Of GTx-024 On Advanced, Androgen Receptor-Positive Triple Negative Breast Cancer (AR+ TNBC)	Compound No.: GTx-024 Author: [name]
---	---

variables for the concentrations by dichotomizing at the median concentration at weeks 16 and 24.

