Although the majority of breast cancers are considered hormone receptor positive (expressing ER, progesterone receptor, or HER2), 15–20% of women diagnosed with breast cancer will have Triple Negative Breast Cancer (TNBC) which is characterized by a lack of expression of ER, progesterone receptor, or HER2. TNBC occurs more frequently in younger patients (< 50 years of age) and generally shows a more aggressive behavior. For those patients with advanced TNBC, standard palliative treatment options are limited to cytotoxic chemotherapy. However, even after initial response to chemotherapy, the duration of the response may be short and there is a higher likelihood of visceral metastases, rapidly progressive disease, and inferior survival compared to hormone positive breast cancer. Therefore, research is focused on identifying therapeutic targets in TNBC. One such target is the androgen receptor (AR). The AR is the most highly expressed steroid receptor in breast cancer with up to 95% of ER+ breast cancers expressing AR. In TNBC, up to 30% of cancers may express AR. Historically, AR has been considered anti-proliferative and beneficial in hormone positive breast cancers. In TNBC, data demonstrates that the presence of AR and androgen synthesizing enzymes is associated with lower proliferation, lower tumor grade, better overall survival, and more favorable clinical outcomes as compared to those patients with TNBC not expressing AR. Evidence also suggests that the AR target gene prostate specific antigen (PSA) is a favorable prognostic marker in breast cancer. Based on these findings, research is focused on AR as a potential therapeutic target.

Protocol: A Phase 2 Open Label, Multi-Center, Multinational Study Investigating The Efficacy and Safety Of GTx-024 On Advanced, Androgen Receptor-Positive Triple Negative Breast Cancer (AR+ TNBC)	Compound No.: GTx-024 Author: [name]
---	---

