### 2.3.2 Potential Benefits

GTx-024 9 mg once daily has been studied in 22 postmenopausal women with metastatic ER+ breast cancer who have previously responded to hormonal therapy. The primary endpoint was assessed in 17 AR positive subjects. Six of these 17 subjects demonstrated CB (SD) at six months. In one subject with SD (RECIST 1.1), tumor regression of 27% was demonstrated. Seven subjects in total (one subject with indeterminate AR status) achieved CB at six months. Among the seven subjects who achieved CB at six months, time-to-progression (TTP) was estimated as 10.2 months. The results also demonstrated that, after a median duration on study of 81 days, 41 percent of all subjects (9/22) achieved CB as best response and also had increased PSA which appears to be an indicator of AR activity. The study is still ongoing with one subject whose disease remains stable beyond 336 days.

Protocol: A Phase 2 Open Label, Multi-Center, Multinational Study Investigating The Efficacy and Safety Of GTx-024 On Advanced, Androgen Receptor-Positive Triple Negative Breast Cancer (AR+ TNBC)	Compound No.: GTx-024 Author: [name]
---	---

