### 3.2.3 Tertiary Efficacy Outcome Measures

The following tertiary efficacy outcome measures apply to both the evaluable subset of the FAS as well as to the FAS:

- Serum PSA at each assessment, changes from baseline to each assessment, and percentage change from baseline of serum PSA at each assessment
- Subject reported QoL (EQ-5D-5L questionnaire) at each assessment and changes from baseline to each assessment
- CTCs at each assessment and changes from baseline to each assessment
- Impact of duration of prior CB on outcome (CB response at weeks 16 and/or 24, PFS, TTP, duration of response)
- Impact of time from diagnosis of metastases to study enrollment on outcome (CB response at weeks 16 and/or 24, PFS, TTP, duration of response)
- Tumor volume at each assessment and change from baseline to each assessment
- Plasma concentrations of GTx-024 and GTx-024 glucuronide on outcome (CB response at weeks 16 and/or 24)

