### **5.4 Treatment Assignment Procedures**

#### **5.4.1 Randomization Procedures**

Not applicable; all subjects will receive GTx-024 at 18 mg daily.

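### Analysing PSA as raw percentage change leans toward an increase when nothing has changed; relative change should be analysed on the log-ratio scale

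*Combined protocol and SAP*

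**What the plan says.** PSA is a tertiary efficacy endpoint, to be analysed in the evaluable subjects and in the Full Analysis Set. Section 3.2.3 lists it in three forms: "Serum PSA at each assessment, changes from baseline to each assessment, and percentage change from baseline of serum PSA at each assessment". The endpoint definition in section 11.4.2 repeats the relative form: "results at each scheduled assessment will be compared to baseline along with percentage change from baseline".

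The analysis in section 11.4.3.4 has two parts. The first carries an explicit test: "PSA changes from baseline to each scheduled assessment will be described and tested for a significant change from baseline". The second is added to it: "Percentage change from baseline will be summarized and analyzed as well". The text does not say whether the summary is a mean or a median, which test is meant, whether PSA is log-transformed, or how unquantifiable values enter. Section 11 leaves further detail on tests to a separate SAP.

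There is no control arm; section 5.4.1 on randomization reads "Not applicable; all subjects will receive GTx-024 at 18 mg daily". On direction, section 2.3.2 says of subjects with clinical benefit in an earlier study that they "had increased PSA which appears to be an indicator of AR activity", and section 2.1 describes evidence that "the AR target gene prostate specific antigen (PSA) is a favorable prognostic marker in breast cancer".

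**The concern.** Percentage change is not symmetric. A subject whose PSA doubles scores +100% and one whose PSA halves scores -50%. The pair averages +25%, although their geometric mean ratio is exactly 1. Random fluctuation around an unchanged level therefore produces a positive mean percentage change.

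Three features make this worth correcting. The shift does not shrink as subjects are added; more subjects only make it easier to declare significant. No control group exists to cancel it. It also points the way the background hopes PSA will move. The two planned PSA analyses could then disagree, with nothing in the plan to say which prevails, and the relative one is the more likely to look positive by artefact.

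**Working it through.** **Inputs.** From the documents: 41 evaluable subjects and at most 55 enrolled (section 11.2), and a single arm (section 5.4.1). No alpha or sidedness is given for PSA, so I take a two-sided 5% test, with 2.5% as the nominal rate of a false increase. The documents give no PSA variability, so the log-ratio SD s is an assumption, taken over the range 0.1 to 0.8.

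**The plan's own figure.** None is stated for PSA. The only sample-size figure, the Simon design for clinical benefit, reproduces: go at 2/21 and success at 5/41 give exact alpha 0.0457 and power 0.902. Nothing below touches it.

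**Expected shift.** Let Z = log(PSA at visit / PSA at baseline), normal with mean 0 and SD s, meaning no drug effect and no drift. Percentage change is P = 100(exp(Z) - 1). Then:

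- mean of P = 100(exp(s²/2) - 1), positive for every s > 0
- median of P = 0

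For s = 0.3, s²/2 = 0.045 and exp(0.045) - 1 = 0.046, that is +4.6%. The sign does not depend on normality: any non-degenerate Z symmetric about zero gives a mean of exp(Z) above 1.

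**Why signed-rank is also affected.** A rise of size z on the log scale has a larger absolute percentage change than a fall of size z. Rises therefore take the higher ranks, and the symmetry that the signed-rank test needs is lost.

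**False-increase rates**, n = 41, 20,000 simulated trials per row, nominal 2.5%:

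| Assumed s | Mean percentage change, no effect | t-test on percentage change | Signed-rank on percentage change |
|---|---|---|---|
| 0.1 | +0.5% | about 4% | 3 to 4% |
| 0.2 | +2.0% | about 7% | 4 to 5% |
| 0.3 | +4.6% | about 12% | about 6% |
| 0.5 | +13.3% | about 23% | about 10% |
| 0.8 | +37.7% | about 44% | about 16% |

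A t-test on Z itself rejects in about 5% of trials two-sided at every s.

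**Dependence on n.** For s = 0.3 / 0.5 / 0.8, the t-test rates at n = 20 are about 6 / 9 / 15% and the signed-rank rates about 4 / 6 / 9%. At n = 55 the t-test rates are about 16 / 34 / 62%.

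**Cross-check with a different parameterisation.** Let each PSA measurement be lognormal with within-subject coefficient of variation c, with errors independent between visits. Then s² = 2 ln(1 + c²), and the mean shift is exactly c². For c = 20%, s² = 2 ln(1.04) = 0.078, so s = 0.28 and the shift is +4%. At n = 41, c = 10 / 20 / 30 / 50% gives t-test rates of 5.2 / 10.2 / 17.7 / 35.1% and signed-rank rates of 3.6 / 5.6 / 8.1 / 13.0%, the same pattern as the table.

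**The other PSA summaries under that second model**, n = 41, c from 10% to 100%, between-subject log-SD 1.0:

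- Absolute change: false increase 1.8 to 1.9% with a t-test and 2.2 to 2.6% with signed-rank. It is balanced between the tails because baseline and follow-up are interchangeable under no effect.
- Sample median percentage change: on average +0.02% to +2.8%.

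**The case against.** The best reply is that the plan has not committed to a biased method. The only PSA analysis with an explicit significance test is change from baseline, which shows no upward shift in the check. Percentage change is an addition with no test named, details of tests are deferred to a separate SAP, and a median would be close to unbiased. All of that stands, and it limits the point. It does not remove it: percentage change is an outcome measure, part of the endpoint definition and a planned analysis, and the wording leaves open the mean and the tests that go wrong.

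The size is also uncertain. At s = 0.1 the mean shift is half a percentage point and the excess error is small. That stands too.

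A reader might infer three stronger things that the documents do not support:

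- That PSA is assessed only, or mainly, as percentage change. The tested absolute change comes first.
- That PSA is the trial's declared pharmacodynamic endpoint. It is listed as a tertiary efficacy endpoint, and it is reductions in SHBG that section 2.2 places among the most sensitive serum biomarkers of AR signalling.
- That the plan would treat a PSA increase as proof of AR activation even if clinical benefit fails. The link in section 2.3.2 is hedged background on an earlier 22-subject ER+ study at 9 mg. Section 11 sets no PSA direction, threshold or decision rule, and the objective in section 3.1 is neutral as to direction.

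**Conclusion.** The concern holds in a limited form. As an inferential scale, raw percentage change is biased toward an increase under no effect, in its arithmetic mean and in t and signed-rank tests on it. The algebra is firm. The size is conditional: slight for a log-ratio SD near 0.1, material from about 0.3 upward, where a t-test at n = 41 gives a false increase in about 12% of trials or more against 2.5%. The rates assume lognormal PSA, no drift, a two-sided 5% test and 41 subjects with data at the visit; with fewer subjects the excess is smaller. The stage 1 rule and the 5/41 criterion are untouched. Because the endpoint is tertiary and the tested absolute change is free of this artefact, the priority is low to moderate.

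**What to change.** In sections 3.2.3, 11.4.2 and 11.4.3.4, and in the SAP:

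- Base inference on relative change on log(PSA at visit / PSA at baseline). Report the geometric mean ratio with its 95% interval, back-transformed to a percentage so that clinical readers still see a familiar figure.
- Keep raw percentage change descriptive only, as median and quartiles or in listings, with no test on it.
- Prespecify how values below quantification are handled, with a sensitivity check. The documents give no assay limit, and a ratio can be driven by the value substituted at baseline.

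The planned analysis of absolute change can stay. No new data, visits or subjects are needed. The cost is a small wording amendment in three protocol sections, changed together so that they do not contradict each other. Under section 14.8 it needs ethics committee approval, so it could travel with another amendment.

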### 7.3 Treatment Phase

The first dose of study drug will be administered at baseline (Visit 2). GTx-024 will be administered for up to 12 months from the first dose of treatment or until disease progression (whichever is sooner), subject's withdrawal of consent, or intolerability. Subjects who benefit from the treatment at week 16 and still benefit from the treatment at week 24 may continue to receive GTx-024 for a total of 12 months from the date of the first dose of study treatment (as long as they still benefit from the treatment during these 12 months). Subjects who continue to demonstrate a beneficial response at 12 months will be offered to continue in a safety extension study under a separate protocol.

After randomization on Day 1, a safety check involving a comprehensive metabolic panel (Chem 14), including serum calcium and liver function tests, will be performed at Week 2 ( $\pm 3$  days). The Week 2 safety check should include a clinic visit. The investigator may repeat these checks at Week 3 ( $\pm 3$  days) if clinically indicated.

During the first 4 months of the treatment phase, the subjects will be asked to come for a visit every 4 weeks (Visits 3, 4, 5, and 6), and then every 8 weeks (Visit 8 and Visits 10–12 as required if still on treatment). Visits 7 and 9 at weeks 20 and 28 will only take place in subjects who have CR or PR at Visit 6 (week 16) or Visit 8 (week 24), respectively (see below).

The following tests and procedures will be performed during Visits 3, 4, 5, 6, and 8 in the treatment phase:

- Review concomitant medications
- Physical examination, including weight and vital signs (heart rate, respiratory rate, body temperature, blood pressure in a sitting position)
- ECOG performance status
- Blood sampling for: hematology, biochemistry, serum lipid profile, coagulation status, serum hormones, and PSA
- Urine analysis, only if clinically indicated
- Urine pregnancy test for premenopausal subjects (at the site)
- AE collection
- Subjects will be asked to complete a QoL questionnaire
- GTx-024 drug accountability/dispensation

Radiologic assessments for anti-tumor effect will be done every 8 weeks whilst subjects receive treatment (Visit 4, Visit 6, Visit 8, and thereafter). In addition, if a subject has CR or PR at Visit 6 (week 16) or Visit 8 (Week 24), in compliance with RECIST 1.1 guidelines, a confirmation of the CR or PR should be done 4 weeks later (i.e., Visit 7 and/or Visit 9, as

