## 7.4 End of Treatment (EOT) Visit

The following tests and procedures will be performed during the EOT visit. For all subjects the EOT visit should happen as soon as possible after the last dose of GTx-024 has been taken and no later than 3 days after that:

- Review of concomitant medications
- Physical examination, including weight and vital signs (heart rate, respiratory rate, temperature, blood pressure in a sitting position)
- ECOG performance status
- Blood sampling for: hematology, biochemistry, serum lipid profile, coagulation status, and serum hormones
- Blood sampling for specific blood tests: PSA and CTCs (enumeration and gene expression)
- Urine analysis, if clinically indicated
- Urine pregnancy test for premenopausal subjects (at the site)
- AE collection
- Radiological evaluation of the breast cancer (as applicable CT/MRI/bone scan). Imaging results will be confirmed by a central imaging facility. The same imaging technique must be used throughout the study in a given subject. The central imaging facility will also perform tumor volumetric assessment for the subjects undergoing CT scanning
- Subjects will be asked to complete a QoL questionnaire

Protocol: A Phase 2 Open Label, Multi-Center, Multinational Study Investigating The Efficacy and Safety Of GTx-024 On Advanced, Androgen Receptor-Positive Triple Negative Breast Cancer (AR+ TNBC)	Compound No.: GTx-024 Author: [name]
---	---

- GTx-024 drug accountability

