#### 11.4.3.7 Missing data/Outliers/Dropout considerations

No imputation for missing data will be carried out other than to complete partial dates using standard imputation techniques as per the Contract Research Organization's (CRO's) standard.

No evaluable subject will have missing data for the primary efficacy analysis because subjects who have the week 16 assessment will be classified as having CB or not, and those who do not have a week 16 assessment will be classified as not having CB.

With regards to missing start and stop dates for AEs and medications, imputation rules will be provided in the SAP. In addition, rules to determine in which period each AE belongs for the summary tables will also be provided in the SAP.

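### The five EQ-5D-5L domains get separate frequency counts at each assessment but no stated within-subject change, so baseline and visit tables can differ only because different subjects remain

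*Combined protocol and SAP*

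**What the plan says.** The endpoint has two parts, values and change. Section 3.2.3 of the protocol gives the outcome measure as "Subject reported QoL (EQ-5D-5L questionnaire) at each assessment and changes from baseline to each assessment". Section 11.4.2, under the tertiary efficacy endpoints, has "QoL will be obtained using the EQ-5D-5L, with each scheduled assessment compared to baseline". Neither sentence confines change to the VAS.

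Section 11.4.3.4 gives the analysis for the evaluable subjects and the FAS. The VAS is summarised at each assessment, and the next sentence reads "Mean changes from baseline will also be summarized using descriptive statistics and 95% confidence intervals". The five single items (mobility, self-care, usual activities, pain/discomfort, anxiety/depression) then have a sentence of their own: they are to be "summarized by means of frequency counts at baseline and at each assessment". It mentions no cross-tabulation with baseline, no improved or worsened category, and no restriction to subjects with both values.

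Three other provisions decide who is in each table:

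- Section 7.3: "GTx-024 will be administered for up to 12 months from the first dose of treatment or until disease progression", whichever is sooner, or until consent is withdrawn or treatment is not tolerated.
- Section 11.4.3.7: "No imputation for missing data will be carried out other than to complete partial dates".
- Section 7.4, for the EOT visit: "Subjects will be asked to complete a QoL questionnaire".

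The Schedule of Events places the EQ-5D-5L at baseline, Visits 3 to 6, Visit 8, Visits 10 to 12 and EOT.

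**The concern.** A domain score is an ordinal level recorded repeatedly in the same subject. One table at baseline and another at a visit drop the link between the two answers, so the reader cannot tell how many subjects moved or in which direction. Ten subjects improving by one level and ten worsening by one level can give the same visit table as twenty subjects who did not move.

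The two tables also cover different people. Baseline includes everyone who started treatment and completed the questionnaire. A later visit includes only those still attending and answering. In advanced disease, subjects with poorer mobility or more pain may well be the ones who leave first. The remaining group then looks healthier than the baseline group even if nobody has improved.

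At stake is the reading of the tertiary objective on QoL. In a single-arm, open-label trial there is no control group whose attrition could be set against that of the treated group, so a falling share with problems is easily credited to the drug.

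**Working it through.** The documents give no sample size, power or precision for the EQ-5D-5L, so there is no planned figure to reproduce. The check has two parts.

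**1. Each part of the endpoint against its stated analysis**

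| Measure | Value at each assessment | Change from baseline |
|---|---|---|
| EQ VAS | descriptive statistics | mean change with 95% CI |
| Five domains | frequency counts | none stated |

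The values half is served for all six measures. The change half has a stated analysis for the VAS only.

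**2. Can attrition alone move the counts?**

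*Count illustration.* Inputs: 41 evaluable subjects (Section 11.2). Assumed: 21 of 41 (51.2%) have moderate or worse problems at baseline, nobody changes level, and retention differs between the 20 with no or slight problems and the other 21. The visit share is (retained with problems) / (all retained).

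| Retention, better / worse group | Retained | Moderate or worse at visit | Shift table |
|---|---|---|---|
| equal | no differential loss | 51.2% | 0 improved, 0 worsened |
| 80% / 60% | 16 + 13 = 29 | 13/29 = 44.8% | 0 improved, 0 worsened |
| 70% / 30% | 14 + 6 = 20 | 6/20 = 30.0% | 0 improved, 0 worsened |
| 50% / 10% | 10 + 2 = 12 | 2/12 = 16.7% | 0 improved, 0 worsened |

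Real worsening can be hidden as well. In the 70%/30% row, if 3 of the 14 better subjects worsen to moderate or beyond, the visit share is (6 + 3)/20 = 45.0%. That still looks better than 51.2%, while a shift table shows 3 worsened and 0 improved.

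*Model illustration.* Assumed: severity Z and dropout propensity W are standard normal with correlation r. A subject is at level 3 or worse when Z > c, with c = 0.126, which gives 45% at baseline. A subject is retained when W < q, with q chosen to give the retained fraction. Nobody changes. The apparent share at the visit is

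P(Z > c | W < q) = P(Z > c and W < q) / P(W < q).

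| Retained | r = 0 | r = 0.2 | r = 0.3 | r = 0.4 |
|---|---|---|---|---|
| 20% (q = -0.842) | 45% | 34% | 29% | 23% |
| 50% (q = 0) | 45% | 39% | 35% | 32% |

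With 20% retained and r = 0.2, for example, the joint probability is 0.068, and 0.068 / 0.20 = 34%. The false improvement at 20% retention is therefore 11, 16 or 22 percentage points, and it is zero at r = 0.

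The 20% figure matches the clinical benefit rate (CBR) under the design's alternative (0.20 x 41 = 8.2, about 8 subjects at week 16), but only as a rough guide to how many remain.

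**The case against.** The case on the other side is that this is a descriptive tertiary measure, described in a section that calls itself an overview.

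- **Detail is deferred.** Section 11 leaves tests, missing-data handling and table specifications to a separate SAP, and none is included in the text supplied. A reader might infer that no paired change will ever be produced, or that the endpoint goes undelivered for five of six measures. The documents do not support that. Section 11.4.3.4 does not mention paired change for the domains, the values half is met, and the SAP may add the rest. The gap in the stated method stands, because that section does name a method for the domains.
- **Early leavers are partly covered.** The questionnaire is given at EOT, and Section 7.6 asks early terminators to attend for the EOT procedures. Tables at each assessment would naturally include EOT. This limits the problem, but an EOT table without the same subjects' baseline still shows no individual change, and no rule links EOT values to the visit tables.
- **CBR is not retention.** It is read centrally and counts a missing week-16 assessment as failure (Section 11.4.2), while treatment decisions follow the investigator (Section 8.1). The 20% retention figure is therefore an assumption, and earlier visits will keep more subjects. This stands, and it limits the size of the artefact but not its direction.
- **No power is lost.** A reader might infer that unpaired tables cost statistical power. The plan tests no domain, so there is no planned power to lose. Nor does the point call for tests: five domains at nine post-baseline assessments in two populations would be 5 x 9 x 2 = 90, and the section states no multiplicity rule.
- **Pairing does not isolate a drug effect.** Shift tables still describe only subjects with both values in an uncontrolled trial. This is true. They remove the false improvement that comes from mixed denominators, not the selection itself.

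**Conclusion.** The point holds as a low-cost improvement to a tertiary, descriptive endpoint. For the five domains the protocol states an analysis of values but none of change, although the endpoint includes both. Comparing the planned tables with each other mixes change within subjects with change in who is left.

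What is established is that the tables can mislead, and that they do so towards apparent improvement when subjects with worse scores leave earlier. How far is not established. The shifts of 11 to 22 points at 20% retention, and 6 to 13 points at 50% (45% to 39%, 35% or 32%), rest on an assumed baseline distribution, retention and correlation, none of which the documents give. If dropping out is unrelated to domain severity, there is no artefact.

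The stage-1 and final efficacy decisions do not use these data and are unaffected.

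**What to change.** In Section 11.4.3.4, and in the SAP, add after the sentence on the single items:

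- For each domain, a shift table of baseline level by level at each assessment among subjects with both values, with EOT shown as the last on-treatment value.
- The numbers improved, unchanged and worsened at each assessment. Exact 95% confidence intervals are optional.
- Beside any visit frequency table, the baseline frequencies of the same subjects and the number who completed the questionnaire.

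No hypothesis tests are needed.

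The cost is a few lines of SAP text and one extra table shell per domain. Nothing new has to be collected. Cells will be sparse at late visits, and the text should state that the tables describe subjects with both values and do not isolate an effect of the drug.
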